Biologic barrier membranes have emerged as a promising adjunct to tendon repair, aiming to modulate the local healing environment rather than relying solely on mechanical or rehabilitative strategies. Experimental and clinical studies have demonstrated that biologic wraps, particularly amniotic membrane-based products, can reduce peritendinous fibrosis and improve functional outcomes after extensor tendon repair, especially in zone VI injuries [8–10]. However, limitations related to availability, processing variability, and regulatory considerations have restricted their widespread adoption. Unlike amniotic membrane, HPTC is a standardized, acellular scaffold with defined composition, consistent degradation kinetics, and a well-established safety record across multiple surgical disciplines.

High-purity type I collagen (HPTC) is a bioengineered, acellular collagen matrix composed of more than 97% pure type I collagen, manufactured to preserve the native triple-helical structure while eliminating immunogenic proteins, elastin, and lipids. Type I collagen is the

principal structural component of native tendon extracellular matrix and plays a central role in cellular adhesion, migration, angiogenesis, and tissue remodeling during healing [11,12]. When processed to high purity, collagen matrices demonstrate excellent biocompatibility, predictable biodegradation, and minimal inflammatory response.

HPTC is flexible, translucent, and easily tailored intraoperatively, allowing it to be fashioned as a loose circumferential wrap or sleeve around repaired tendons without increasing bulk or restricting tendon gliding. Preclinical studies have shown that collagen–glycosaminoglycan scaffolds can significantly reduce early postoperative tendon adhesions while preserving tensile strength and intrinsic healing [13,14]. These findings provide a strong biological rationale for the use of HPTC as a peritendinous barrier in tendon repair.

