### **Randomization, Allocation Concealment, and Blinding**

Eligible patients were randomized in a 1:1 ratio to the experimental or control group using a computer-generated randomization sequence with variable block sizes of four and six. The randomization sequence was prepared by an independent statistician not involved in patient care.

Allocation concealment was ensured using sequentially numbered, opaque, sealed envelopes, which were opened in the operating room after confirmation of eligibility and completion of tendon exposure. Due to the nature of the intervention, blinding of the operating surgeon and patient was not feasible. However, outcome assessors, including hand therapists performing functional measurements and clinicians evaluating outcomes, were blinded to group allocation. The data analyst was also blinded to treatment assignment.

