### **Surgical Technique**

All procedures were performed under regional or general anaesthesia with tourniquet control. The affected upper limb was positioned on a hand table, and standard sterile preparation and draping were performed. A dorsal longitudinal or zig-zag incision was made over the injured extensor tendon, incorporating the traumatic wound where feasible.

The extensor tendon ends were identified, and devitalized tissue was carefully debrided while preserving maximal tendon length. The tendon was mobilized sufficiently to allow tension-free repair, taking care to minimize disruption of surrounding paratenon and soft tissues.

Primary tendon repair was performed using a standardized core suture technique, typically a modified Kessler or four-strand repair, with nonabsorbable monofilament suture material (4-0). The core repair was reinforced with a circumferential running epitendinous suture using fine monofilament suture (6-0) to improve repair strength and smooth the tendon surface.

In the experimental group, following completion of the tendon repair and before skin closure, a sterile HPTC (Surgicoll-Mesh®) sheet was hydrated in normal saline according to manufacturer instructions. The membrane was cut into a rectangular strip measuring approximately 2 to 4 cm in length and 1 to 1.5 cm in width, tailored to the diameter of the repaired tendon. The HPTC strip was wrapped circumferentially around the repair site as a loose sleeve, ensuring overlap of approximately 2 to 3 mm at the edges. The wrap was secured using cyanoacrylate tissue adhesive, applied to the overlapping edges of the collagen membrane and sparingly to the epitenon (Figures 1 & 2). Care was taken to avoid constriction, folding, or bulk that could impede tendon gliding, particularly beneath the

extensor retinaculum in zone VII. Gentle passive flexion and extension were performed intraoperatively to confirm smooth tendon excursion and absence of mechanical block. In the control group, no biologic wrap or anti-adhesive adjunct was applied after tendon repair. Skin closure, dressing, and splinting were identical in both groups.

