### **Outcome Measures**

The primary outcome measure was total active motion of the involved digit or digits at eight weeks postoperatively. Total active motion was calculated as the sum of active flexion at the metacarpophalangeal, proximal interphalangeal, and distal interphalangeal joints minus extension deficits. Results were expressed in degrees and as a percentage of the contralateral uninvolved digit or standardized normative values.

Secondary outcomes included QuickDASH scores at six and eight weeks, extensor lag at individual joints measured in degrees at eight weeks, grip strength measured using a calibrated Jamar dynamometer at eight weeks, incidence of adhesion-related events including failure to achieve functional motion thresholds or need for tenolysis, complication rates, time to return to work or activities of daily living, and patient satisfaction scores (Table 1).

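### The reason given for leaving patients unblinded fits the surgeon but is not justified for the patient, whose effort or report drives the primary and most secondary outcomes

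*Combined protocol and SAP*

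**What the plan says.** All places are in the combined protocol and SAP.

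- **Randomization, Allocation Concealment, and Blinding.** One reason covers two parties: "Due to the nature of the intervention, blinding of the operating surgeon and patient was not feasible". The same section says that "outcome assessors, including hand therapists performing functional measurements and clinicians evaluating outcomes, were blinded to group allocation", and that "The data analyst was also blinded to treatment assignment". Envelopes are "opened in the operating room after confirmation of eligibility and completion of tendon exposure".
- **Surgical Technique.** "All procedures were performed under regional or general anaesthesia with tourniquet control". In the experimental arm the collagen sheet is hydrated, cut, wrapped around the repaired tendon and glued before the skin is closed. Controls receive no wrap. "Skin closure, dressing, and splinting were identical in both groups".
- **Introduction.** The material is described as one that can be fashioned around a tendon "without increasing bulk or restricting tendon gliding".
- **Postoperative Splinting and Rehabilitation Protocol.** Both arms follow the same standardized programme under certified hand therapists. The section does not say whether the supervising therapists are the blinded ones who take the measurements.
- **Outcome Measures.** The primary outcome is total active motion at eight weeks. "Secondary outcomes included QuickDASH scores at six and eight weeks", and also extensor lag, grip strength, adhesion-related events, complications, return to work or daily activities, and satisfaction.

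**The concern.** The surgeon cannot be blinded to a sheet that he or she wraps around a tendon. The patient is in a different position, and the plan gives no separate reason for the patient. After the operation, nothing in the described care differs visibly between the arms. On the text as written, the patient learns the allocation by being told, or by seeing or hearing it in theatre.

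Two things are at stake. First, a patient who knows that he or she received an anti-adhesion wrap, or knows that it was withheld, may exercise, try harder at testing or report differently. The likely direction is that of the hypothesis. A blinded person holding the goniometer does not remove this, because the motion being measured is active. Second, the assessor blinding rests on the patient saying nothing. The plan describes no instruction to patients and no check of whether blinding held.

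**Working it through.** **Step 1: cues to the patient, stage by stage.**

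| Stage | Difference between arms in the text | Could the patient notice? |
|---|---|---|
| Envelope opened in theatre after tendon exposure | Allocation becomes known to the team | Not under general anaesthesia; possibly if awake under regional block |
| Sheet hydrated, cut, wrapped and glued | Experimental arm only | Same |
| Closure, dressing, splint | None | No cue described |
| Rehabilitation | None | No cue described |

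The only described cues are in theatre, and they can reach only patients who are awake. Sedation, screening of the field and what staff say aloud are not described.

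**Step 2: which outcomes run through the patient.**

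| Outcome | Depends on patient effort or report? |
|---|---|
| Total active motion (primary) | Yes: assessor measures, patient performs |
| Extensor lag, grip strength | Yes: performed by the patient |
| QuickDASH, satisfaction | Yes: self-reported |
| Return to work or daily activities | Largely: influenced by the patient |
| Adhesion-related events: motion threshold | Yes: derived from motion |
| Adhesion-related events: need for tenolysis | No: a clinical decision; the plan does not say whose |
| Complications | Safety outcome, not counted here |

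**Step 3: the plan's own figure.** Inputs from Sample Size Calculation: standardized effect 0.75, two-sided alpha 0.05, power 80%.

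n per group = 2 × [(1.960 + 0.842) / 0.75]² = 27.91, rounded up to 28. This reproduces the stated minimum. The exact t-test gives 28.90, rounded up to 29, so the planned 30 per group is sufficient under either method before any loss to follow-up. Blinding patients does not change this number.

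**Step 4: sensitivity to a spurious shift.** The documents give no bias size, so the shifts b are assumed. Suppose that the wrap has no true effect and that expectation moves mean total active motion by b SD in its favour. With n = 30 per arm:

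- degrees of freedom = 2 × 30 − 2 = 58; two-sided 5% critical value = 2.002;
- noncentrality = b × √(n/2) = b × √15 = 3.873b;
- rejection probability = P(|T| > 2.002), with T noncentral t on 58 df.

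| Assumed b (SD) | Share of the planned 0.75 | Noncentrality | Two-sided rejection | Of which favouring the wrap |
|---|---|---|---|---|
| 0 | 0% | 0 | 5.0% | 2.5% |
| 0.1 | 13% | 0.387 | 6.7% | 5.7% |
| 0.25 | 33% | 0.968 | 15.9% | 15.7% |
| 0.4 | 53% | 1.549 | 33.2% | 33.1% |

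At 28 per arm the two-sided figures are 6.6%, 15.1% and 31.2%.

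**The case against.** **A reader might infer that the documents prove patient blinding to be feasible.** They do not. Regional anaesthesia is allowed, so some patients may be awake when the envelope is opened and the sheet is prepared. Screening and theatre communication are not described. Nor do the documents settle whether a wrap can be felt through the skin. The no-bulk wording is a product description in the Introduction, while Surgical Technique treats bulk as something to take care to avoid, and the Introduction itself calls the dorsal soft tissue thin. What stands is narrower: the stated reason does not justify leaving the patient unblinded after surgery.

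**A reader might infer that every efficacy outcome depends on the patient.** Need for tenolysis does not. It is a clinical decision, where the surgeon's knowledge of the arm may matter instead.

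**Existing safeguards count.** Measuring therapists, evaluating clinicians and the analyst are blinded, which limits measurement and analysis bias. Rehabilitation is standardized and supervised, which narrows the exercise-adherence route. Nothing in the documents shows that patients disclosed their arm. This lowers the expected bias, but it does not reach effort at testing or self-report, and it leaves assessor blinding dependent on the patient's silence.

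**The magnitude is hypothetical.** The arithmetic is right, but no passage shows that patient knowledge moves total active motion by 0.1 SD or by 0.4 SD. At the low end the effect is minor. This objection stands in full, and the figures should not be read as an estimate.

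**The trial may already be under way or complete.** Much of the text is in the past tense, although the Statistical Analysis Plan mixes tenses. If patients have been treated unblinded, rewriting the section would misdescribe what was done. This stands and decides which form of the fix applies.

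**Conclusion.** The concern holds in this form: the plan gives a reason that is valid for the surgeon, extends it to the patient without support, and thereby leaves the primary outcome and most secondary outcomes open to a directional bias that assessor and analyst blinding cannot remove. It weakens confidence in the result without invalidating the trial, because randomization, concealed allocation and blinded measurement remain.

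The size is unknown. Under assumed shifts of 0.1 to 0.4 SD, no true effect, 30 per arm and a t-test, the false-positive rate would lie between about 6.7% and 33.2% instead of 5%. The conclusion does not rest on any one of these values. It rests on the absence of a described postoperative cue, and on the outcomes being performed or reported by the patient.

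**What to change.** **If patients are still to be treated**, change Randomization, Allocation Concealment, and Blinding along these lines:

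- Patients, treating therapists and outcome assessors are blinded until the 8-week visit; only the operating team is not.
- When a patient is awake under regional block, the field is screened and the allocation is not announced aloud.
- Allocation is kept out of the therapy referral and patient-facing papers. The implant is entered in a restricted record, with an unblinding route for clinical need.
- At week 8, patient and assessor each record which arm they believe the patient was in.

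The cost is theatre discipline, revised consent wording and restricted documentation of the implant. No extra patients, visits or procedures are needed.

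**If patients have already been treated unblinded**, do not rewrite the conduct. Correct the justification so that it applies to the surgeon and states why patients were in fact told or not shielded. Report what patients and therapists knew. State expectation bias as a limitation on the conclusions for total active motion and the patient-reported outcomes. This costs only text.

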### **Surgical Technique**

All procedures were performed under regional or general anaesthesia with tourniquet control. The affected upper limb was positioned on a hand table, and standard sterile preparation and draping were performed. A dorsal longitudinal or zig-zag incision was made over the injured extensor tendon, incorporating the traumatic wound where feasible.

The extensor tendon ends were identified, and devitalized tissue was carefully debrided while preserving maximal tendon length. The tendon was mobilized sufficiently to allow tension-free repair, taking care to minimize disruption of surrounding paratenon and soft tissues.

Primary tendon repair was performed using a standardized core suture technique, typically a modified Kessler or four-strand repair, with nonabsorbable monofilament suture material (4-0). The core repair was reinforced with a circumferential running epitendinous suture using fine monofilament suture (6-0) to improve repair strength and smooth the tendon surface.

In the experimental group, following completion of the tendon repair and before skin closure, a sterile HPTC (Surgicoll-Mesh®) sheet was hydrated in normal saline according to manufacturer instructions. The membrane was cut into a rectangular strip measuring approximately 2 to 4 cm in length and 1 to 1.5 cm in width, tailored to the diameter of the repaired tendon. The HPTC strip was wrapped circumferentially around the repair site as a loose sleeve, ensuring overlap of approximately 2 to 3 mm at the edges. The wrap was secured using cyanoacrylate tissue adhesive, applied to the overlapping edges of the collagen membrane and sparingly to the epitenon (Figures 1 & 2). Care was taken to avoid constriction, folding, or bulk that could impede tendon gliding, particularly beneath the

extensor retinaculum in zone VII. Gentle passive flexion and extension were performed intraoperatively to confirm smooth tendon excursion and absence of mechanical block. In the control group, no biologic wrap or anti-adhesive adjunct was applied after tendon repair. Skin closure, dressing, and splinting were identical in both groups.

**Figure 1: Showing surgical technique of repaired extensor tendon (single) wrap with HPTC**

Image showing repaired extensor digitorum to index finger in zone 6 (Left). Image showing HPTC wrap around the repaired tendon (Right)

**Figure 2: Showing surgical technique of multiple repaired extensor tendon wrapped with HPTC**

Image showing repaired extensor digitorum communis tendons in zone 8 (Left). Image showing HPTC wrap around the repaired tendons (Right)

### **Postoperative Splinting and Rehabilitation Protocol**

All patients were placed in a standardized dorsal protective splint with the wrist in extension and the metacarpophalangeal joints positioned according to the involved zone and institutional extensor tendon protocol. Postoperative rehabilitation was standardized across both groups and supervised by certified hand therapists.

Initial immobilization was maintained for five to seven days. Controlled early active or early controlled motion protocols were then initiated based on institutional standards for zones VI–VIII, progressing to increased range of motion exercises by three to four weeks and gradual strengthening by six weeks. No additional anti-adhesion agents or topical products targeting tendon healing were permitted during the study period.

### **Outcome Measures**

The primary outcome measure was total active motion of the involved digit or digits at eight weeks postoperatively. Total active motion was calculated as the sum of active flexion at the metacarpophalangeal, proximal interphalangeal, and distal interphalangeal joints minus extension deficits. Results were expressed in degrees and as a percentage of the contralateral uninvolved digit or standardized normative values.

Secondary outcomes included QuickDASH scores at six and eight weeks, extensor lag at individual joints measured in degrees at eight weeks, grip strength measured using a calibrated Jamar dynamometer at eight weeks, incidence of adhesion-related events including failure to achieve functional motion thresholds or need for tenolysis, complication rates, time to return to work or activities of daily living, and patient satisfaction scores (Table 1).

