### **Study Population**

Adult patients aged 18 to 65 years presenting with acute extensor tendon injuries of the hand involving zones VI, VII, and/or VIII were screened for eligibility. Only patients with complete extensor tendon lacerations involving at least 50% of the tendon cross-sectional area and requiring primary repair were considered for inclusion. Surgical repair was required to be performed within 72 hours of injury.

Patients with crush or avulsion injuries, segmental tendon loss requiring grafting or tendon transfer, associated open fractures requiring dorsal plating across the repair site, prior surgery or significant scarring in the region, major associated nerve injuries requiring grafting, uncontrolled systemic illness, active infection, known hypersensitivity to collagen, pregnancy, or inability to comply with postoperative rehabilitation were excluded.

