## **Statistical Analysis Plan**

All analyses were performed using an intention-to-treat approach, including all randomized participants in their allocated groups. A per-protocol analysis will be conducted as a secondary exploratory analysis.

Continuous variables were expressed as mean  $\pm$  standard deviation or median with interquartile range, depending on distribution. Categorical variables will be expressed as frequencies and percentages. Between-group comparisons of the primary outcome were performed using an independent samples t-test for normally distributed data or the Mann–Whitney U test for non-normally distributed data. Proportions of patients achieving good or excellent functional outcomes based on established extensor tendon scoring systems were compared using chi-square or Fisher’s exact tests.

Secondary outcomes were analysed using appropriate parametric or non-parametric tests. Repeated-measures analysis of variance or mixed-effects models was used to evaluate changes in functional scores over time. Effect sizes were reported using Cohen’s d for continuous outcomes and relative risk or odds ratios for categorical outcomes, with corresponding 95% confidence intervals. Two-sided p-values less than 0.05 was considered statistically significant.

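### Grip strength has no stated reference hand, norm or covariate, so its week-8 comparison would probably lose precision, by an amount the documents do not allow one to fix

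*Combined protocol and SAP*

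**What the plan says.** Grip is a secondary outcome. The Outcome Measures section gives the instrument and the time point, "grip strength measured using a calibrated Jamar dynamometer at eight weeks", and Table 1 repeats the single week-8 assessment. Neither place states the hand, the unit, a baseline value, or a comparison with the other hand or with norms.

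For TAM, the same section does give a reference: "Results were expressed in degrees and as a percentage of the contralateral uninvolved digit or standardized normative values".

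The Study Population section admits "Adult patients aged 18 to 65 years presenting with acute extensor tendon injuries of the hand". It states no sex restriction, and pregnancy is among the exclusions ("known hypersensitivity to collagen, pregnancy, or inability to comply with postoperative rehabilitation were excluded"), so women are eligible by implication. The randomisation section describes blocks of four and six and states no stratification.

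On analysis, the Statistical Analysis Plan says: "Secondary outcomes were analysed using appropriate parametric or non-parametric tests". It names no covariate for any outcome. It adds "Repeated-measures analysis of variance or mixed-effects models was used to evaluate changes in functional scores over time", but grip has one time point, so that sentence supplies no adjustment for it.

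**The concern.** Grip can be expected to differ between men and women, across a 47-year age span, and from person to person for reasons unrelated to the injury. If week-8 grip is compared between arms with no reference hand and no covariates, all of that variation sits in the error term. Part of it could be removed with information that is on file or easily obtained. For TAM the authors gave a within-person or normative reference; for grip they gave none.

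At stake is the precision of one secondary outcome in a trial of 60 patients, and clarity about which grip analysis will be reported. Because scale and adjustment are open, kilograms, percentage of the other hand, or an adjusted difference could each be chosen after the data are seen. The primary conclusion on TAM is not affected.

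**Working it through.** **1. The plan's own figure.** Sample Size Calculation section: effect size 0.75, two-sided alpha 0.05, power 80%.
n per arm = 2(1.960 + 0.842)² / 0.75² = 27.9, so 28, as stated. The noncentral t calculation gives 28.9, so 29. The plan recruits 30 per arm. This calculation is for TAM; none is given for grip.

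**2. What 30 per arm resolves for grip, unadjusted.** Detectable difference at 80% power = (1.960 + 0.842) × √(2/30) = 0.72 SD of grip. Power for a true difference of 0.75 SD is 82.8% (normal) or 81.5% (t). For 0.5 SD it is 49.1% or 47.8%. The documents give neither effect size for grip.

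**3. Share of variance due to sex (assumed inputs).** Let p be the proportion of men and D the male–female gap in within-sex SDs. Sex adds v = p(1−p)D² to a within-sex variance of 1. Its share is f = v/(1+v), and removing it is worth 1/(1−f) = 1+v times the patients.

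| p | D | v | f | equivalent patients | detectable difference, raw SD |
|---|---|---|---|---|---|
| 0.85 | 1 | 0.1275 | 11.3% | ×1.13 | 0.72 × √(1/1.1275) = 0.68 |
| 0.60 | 2 | 0.96 | 49.0% | ×1.96 | 0.72 × √(1/1.96) = 0.52 |

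**4. The same idea in kilograms (all values assumed).** Total SD = √(s² + q(1−q)g²), where s is the within-sex SD, g the sex gap and q the proportion of women. Power is for a true difference of 5 kg with 30 per arm, normal approximation.
- Small loss: s = 9, g = 10, q = 0.1. Total SD = √(81 + 9) = 9.49 kg. Power is 53% unadjusted and 58% adjusted for sex.
- Large loss: s = 7, g = 20, q = 0.5. Total SD = √(49 + 100) = 12.21 kg. Power is 35% unadjusted and 79% adjusted.
- Over the whole grid (s of 7 or 9 kg; g of 10, 15 or 20 kg; q of 10% to 50%), unadjusted power runs from 30% to 72% and adjusted power from 58% to 79%.

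**5. Adding opposite-hand grip (assumed correlation r).** The residual SD falls by √(1−r²), so a 0.5 SD difference becomes 0.5/√(1−r²) residual SDs. Power by the t calculation with 30 per arm:
- no adjustment: 47.8%
- r = 0.5: 0.5/0.866 = 0.577, 59.4%
- r = 0.7: 0.5/0.714 = 0.700, 76.0%
- r = 0.8: 0.5/0.600 = 0.833, 88.8%

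Steps 3 to 5 ignore the few degrees of freedom that the covariates use, so at the low end part of the gain would be given back. The direction of the effect follows from the design. Its size rests wholly on assumed inputs.

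**The case against.** The strongest reply is that the plan is silent rather than wrong. It does not say that grip is compared as an unscaled value. The t-test and Mann–Whitney test are named for the primary outcome only, and the wording for secondary outcomes does not exclude ANCOVA. That is correct. A reader might infer that the plan commits grip to an unadjusted two-sample test in kilograms; the documents do not say so. What stands is that no reference and no covariate is specified, so nothing in the plan removes this variation.

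A reader might also infer that between-person variation overwhelms any treatment difference, or that a real grip benefit will probably be missed. Neither can be shown. The documents give no grip SD, sex mix, expected difference or between-hand correlation. Under assumed inputs the loss runs from about 5 power points to more than 40, and at 0.75 SD an unadjusted comparison would already have about 82% power.

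Nor does a chance imbalance in sex invalidate the test. Sex variation also enters the SD used in the test, so the 5% error rate and the confidence interval already allow for such imbalance.

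Two further points are fair. Adjustment is equally unstated for TAM, although TAM does have a reference. And opposite-hand grip at week 8 is measured after randomisation, so it is a sound covariate only if treatment does not affect that hand.

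**Conclusion.** The point holds as a modest, inexpensive improvement to a secondary outcome. Unlike TAM, grip has no stated reference, and the Statistical Analysis Plan names no covariate. A week-8 comparison made as written would therefore probably lose precision to sex, age and person-to-person differences. It would remain unbiased, with a valid error rate.

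The size of the loss cannot be determined from the documents. With 60% to 85% men and a sex gap of 1 to 2 within-sex SDs, both assumed, removing the sex component alone is worth 1.13 to 1.96 times the patients. The eligibility of women is inferred from the pregnancy exclusion.

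**What to change.** Prespecify one grip analysis before the data are compared by arm: ANCOVA of injured-hand grip at week 8, with arm, centre, sex and age in the model, reporting the adjusted difference in kg with its 95% CI.

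Where opposite-hand grip is taken with the same dynamometer at the same visit, add it as a covariate. The SAP should then state:
- the assumption that the wrap does not affect the uninjured hand;
- how hand dominance is handled, for example by an indicator for injury to the dominant hand;
- what is done when both hands are injured and there is no uninjured reference.

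If opposite-hand grip was not taken, keep the sex and age adjustment.

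The cost is one SAP sentence and about one minute per patient for a second reading at an existing visit. The sex and age adjustment should need no new data: age is an eligibility criterion, and sex is needed to apply the pregnancy exclusion. The Data Collection and Management section does not list the recorded variables, so this should be confirmed against the case report form.
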